states will be treated as random effects because Medicaid expansion may vary across clinics and states. However, we recognize that the assumption for random effects may not be met and we will also assess the robustness of our assumptions by running models that treat clinics and states as fixed effects. We will formally test the validity of the random effects using the standard Hausman test¹⁷⁴ and assess overall qualitative differences that may arise between the random and fixed effects models.

We will use GLMM,¹⁷³ which offer flexible regression modeling to accommodate different sources of correlations (serial, intra-clinic, and intra-state), categorical and continuous covariates, and fixed and time-dependent covariates. These methods offer a wide range of parametric distributions to model the dependent variables, including logistic regression (binary data), beta regression (percent data), Poisson regression (count data), and Gaussian regression (normally distributed data). For example, to assess a change in services utilized, a logistic mixed-effects regression model can analyze services received in pre- and post-expansion periods as a function of whether a patient belongs to CHC in a state that did or did not expand Medicaid and other possible confounders (e.g., predisposing factors; need for services). The distribution of the outcomes of interest will be examined before selecting an analysis model; specific models will be refined through an iterative process, guided by the hypotheses, conceptual model, and preliminary analyses. If we find significant patient panel or clinic differences in states that did or did not expand Medicaid (Aim 1) or in patients who are newly insured, already insured, and uninsured (Aim 2), we will use propensity score weighting methods to reduce the observed bias, help minimize external threats to the validity of the results and adjust for imbalances between intervention and comparison clinics.¹⁷⁴ [name] (PhD biostatistician) will lead these decisions and determine the need for additional models.

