Methods to account for non-users in the post-period. The available data do not indicate whether patients without clinic contact in the post-period are true non-users, or drop-outs (*i.e.*, left the clinic permanently to seek care elsewhere), potentially leading to underestimated utilization rates. A dropout rate that is similar across groups will not impact the comparison between clinics in expansion versus non-expansion states or between patients with different coverage status, but differential dropout poses a threat to the generalizability of the findings. As a sensitivity analysis, we will use pre-expansion data to model the probability that a patient has a visit in year t based on demographic information and the number of visits to the clinic in year $t-1$ and $t-2$. Parameters from this model will be used to attach a weight to all patients across all years. This method provides a measure of the contribution of each patient on utilization measures and avoids bias that may arise from defining patient attribution according to utilization patterns that occur because of the Medicaid expansion.

Standard errors adjustments. Depending on the distribution of the outcomes of interest, standard errors may be difficult to estimate using standard regression variance output. Thus, we plan to implement bootstrapping to obtain reliable standard errors when appropriate. Additionally, as a sensitivity analysis, we plan to bootstrap all analytic models simultaneously to allow estimating covariances among parameter estimators across models.

Power calculations. For **Aim 1**, our total sample size includes 761,840 patients distributed over

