442 clinics in 16 states. We estimated power accounting for the clustering of patients within clinics and clinics within states. This sample size will provide 90% power in patient-level analyses to detect a minimum of 1.9% difference in changes in binary outcomes before and after Medicaid expansion, when intra-cluster correlation (ICC) is set to 0.10.¹⁷⁵ For example, this corresponds to a scenario where the pre- and post-expansion change of percent of covered visits is +6.0% in the Medicaid expansion group and +4.1% in the non-Medicaid expansion group assuming an ICC=0.10. As most studies show an ICC<0.001,¹⁷⁵ the proposed study will have sufficient power to detect differences of health policy importance. We will also have 90% power to detect a 2.7% difference in changes of binary outcomes, assuming an even more conservative ICC=0.20. For clinic-level analyses, this sample size will provide 90% to detect a minimum of 2.3% difference in binary outcomes before and after Medicaid expansion with an ICC=0.10. For continuous outcomes, the study sample will provide 90% to detect a 0.26 difference in change in mean before and after Medicaid expansion (ICC=0.10). This corresponds to a scenario where the pre- and post-expansion change is +0.30 for clinics in expansion state and +0.04 for clinics in non-expansion state. For **Aim 2**, with a sample size of 447,488 patients, the comparisons of newly insured compared to already insured and uninsured will have 90% power to detect a difference of 3.35%. For example, this corresponds to a scenario where newly insured patients increased covered visits +4.55% (pre vs. post) and only +1.2% increase in covered visits for already insured from pre to post. For **Aim 3** (sample size of 187,684), a comparison of newly insured versus already insured will have 90% power to detect difference in changes in binary outcomes before and after Medicaid expansion of 2.8% assuming an ICC=0.10. Estimates of parameters for all of these power calculations were obtained from a preliminary pull of OCHIN EHR data. **We note that power calculations estimate the minimum numbers needed to detect changes. In reality, the impact of Medicaid expansion could be much greater than these minimums.** Although these calculations are simplistic and do not account for all differences among clinics or propensity score matching, we expect our actual analyses will have a similar or greater power as regression adjustment results in increased precision for certain outcomes and thus increased statistical power.¹⁷⁶

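### The SAP's claim that similar dropout leaves the group comparison unaffected holds only for rate-ratio contrasts; additive and logit difference-in-differences are distorted

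*SAP*

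**What the plan says.** The SAP's paragraph in B.4.4 on non-users in the post-period starts from a data limit: "The available data do not indicate whether patients without clinic contact in the post-period are true non-users, or drop-outs". It gives the consequence as "potentially leading to underestimated utilization rates". It then says "A dropout rate that is similar across groups will not impact the comparison between clinics in expansion versus non-expansion states", and extends this to comparisons between coverage groups. No scale or other condition is attached. Only unequal dropout is treated as a problem, in these words: "differential dropout poses a threat to the generalizability of the findings".

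A sensitivity analysis follows. A model fitted to pre-expansion data predicts a visit from demographics and earlier visits, and "Parameters from this model will be used to attach a weight to all patients across all years".

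The scale of analysis is left open. B.4.4 lists logistic, beta, Poisson and Gaussian models. Its worked example for utilization is on the logit scale: "to assess a change in services utilized, a logistic mixed-effects regression model can analyze services received in pre- and post-expansion periods". The power paragraph states its targets as differences in changes; for continuous outcomes, "the pre- and post-expansion change is +0.30 for clinics in expansion state and +0.04 for clinics in non-expansion state".

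B.4.6, item 2, separately expects data to be missing for patients who sought care outside the network, possibly not at random. It plans covariate modeling, multiple imputation if missingness is non-trivial, and a comparison of completers with all patients, with and without imputation.

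**The concern.** By the SAP's own account, dropout lowers recorded post-period use. A common dropout fraction then scales down both groups' post-period means and leaves the pre-period means alone. A common multiplier cancels from a ratio of ratios. It does not cancel from a difference of differences, or from a difference of log-odds.

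The sentence therefore reassures on scales where it is wrong. A team that found similar no-contact rates could report an additive or logistic DID as unaffected by dropout. That DID could in fact be shrunk, inflated or shifted away from zero. Utilization and receipt of preventive services are primary dependent variables for Aims 1 and 2, so the point reaches main results wherever those outcomes are analyzed on such a scale.

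**Working it through.** The disputed sentence carries no figure to reproduce. The plan's continuous contrast does reproduce: 0.30 − 0.04 = 0.26.

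**Inputs**
- Changes of +0.30 and +0.04: SAP, power calculations. The outcome and unit are not stated; here they are treated as annual visits per patient (assumption).
- Visits and patients: protocol, Data Sources. Expansion 2,600,000 / 499,719 = 5.20 per patient; non-expansion 1,500,000 / 370,600 = 4.05. The gap is 1.155 before rounding. Over one pre-year and two post-years this is 1.73 versus 1.35 per year, a gap of 0.385. These are whole-period averages; using the gap as a baseline gap is an assumption.
- Dropout d: not in the documents. Assumed 10% and 20%, equal in both groups, unrelated to use, post-period only, with no-contact patients kept as zero use.

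**Additive scale.** Let E0, E1 be the true pre and post means in expansion states and C0, C1 those in non-expansion states.

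Observed DID = [(1−d)E1 − E0] − [(1−d)C1 − C0] = true DID − d(E1 − C1).

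| Expansion baseline relative to non-expansion | True DID | E1 − C1 | Observed, d = 10% | Observed, d = 20% |
|---|---|---|---|---|
| Equal | 0.26 | 0.26 | 0.26 − 0.026 = 0.234 | 0.26 − 0.052 = 0.208 |
| Higher by 0.385 | 0.26 | 0.645 | 0.26 − 0.0645 = 0.196 | 0.26 − 0.129 = 0.131 |
| Lower by 0.385 | 0.26 | −0.125 | 0.26 + 0.0125 = 0.273 | 0.26 + 0.025 = 0.285 |
| Higher by 0.385, no effect | 0 | 0.385 | −0.039 | −0.077 |

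If the visit totals cover the four years 2012–2015, which the protocol also gives as the study period, the gap is 1.155 / 4 = 0.289. The second row then reads 0.26 − 0.1 × 0.549 = 0.205 and 0.26 − 0.2 × 0.549 = 0.150.

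For the equal-baseline row, assume an unchanged standard error and a two-sided 5% test. Power is Φ[(1.960 + 1.282)(1−d) − 1.960], so a nominal 90% falls to 83% at d = 10% and 74% at d = 20%.

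**Log scale.** log[(1−d)E1] − log[(1−d)C1] = log E1 − log C1. The factor cancels and the bias is zero.

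**Logit scale.** Bias = h(E1) − h(C1), with h(p) = log{(1−d)(1−p) / [1 − (1−d)p]}. It is zero only if E1 = C1. Example (assumed): baselines 50% and 40%, a common log-odds shift of 0.2, so no true effect and post levels of 0.550 and 0.449. At d = 20%, h(0.550) = −0.442 and h(0.449) = −0.374. The bias is −0.068, an odds ratio of 0.935 where the truth is 1. At d = 10% it is 0.964.

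**The case against.** Several points on the other side have force.

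- **Most visit-rate papers are on the safe scale.** The protocol's analysis tables use rate ratios, DID ratios or Poisson models for the 24-month coverage paper, the 2013–2014 utilization paper and both diabetes visit papers. Equal, non-informative dropout cancels there. A reader might infer that all the visit results are compromised; the documents do not support that.
- **Attrition bias is not ignored.** A reader might infer that the SAP sees dropout only as a matter of generalizability, or tells the team to stop once dropout looks similar. B.4.6 speaks of bias from differential attrition and plans completer and imputation comparisons, the visit-probability weighting is planned regardless, and no stopping rule exists. These plans soften the problem but do not repair it. Imputation and completer analyses need to know whose data are missing, and B.4.4 says drop-outs cannot be identified. Weights from a pre-expansion model need not remove a factor that arises only post-expansion. Since the SAP does not say whether visit history is updated each year, one cannot assert that they leave all of it.
- **The covered-visits power example is not affected this way.** It is tempting to apply the formula to the +6.0% versus +4.1% scenario and find a sign reversal. That outcome is a share of visits, so a departed patient leaves both numerator and denominator.
- **A bias larger than the 0.26 target is not shown.** With no true effect and 10% versus 20% dropout, the additive bias at a common level is 0.1 × level. At 1.35 to 1.73 visits per year this is 0.14 to 0.17. Exceeding 0.26 would need a level above 2.6, which the visit totals do not suggest.
- **The pre-period may not be untouched.** Inclusion needs only one visit in the study period, so patients first seen after expansion can add pre-period zeros. If both periods were diluted by the same fraction, the shift would vanish and only the (1−d) shrinkage remain. The post-only assumption fits best where a pre-period visit is required, as in the protocol's cohort of patients uninsured before the ACA, analyzed by ordinal logistic regression.
- **Care elsewhere may be a true zero** if the target is visits to the study clinics. That is arguable for visits, less so for receipt of preventive services, and the SAP itself calls the result an underestimate.

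**Conclusion.** The sentence is wrong as written and needs a condition. With no-contact patients counted as non-users, similar dropout leaves the comparison unchanged only for rate-ratio contrasts with non-informative dropout. On the additive scale the DID moves by −d times the true post-period gap; on the logit scale it moves unless post-period levels are equal. The exposed analyses are mainly patient-level binary or ordinal utilization and service-receipt outcomes and any Gaussian outcome.

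Under the assumptions listed, a true 0.26 is reported as anything from 0.131 to 0.285, and a true zero with a post-period gap of 0.385 as about −0.04 to −0.08. These figures show that the effect is not negligible at plausible inputs. They do not estimate the bias in any PACE result, because the documents give neither dropout rates nor baseline levels. The algebra itself needs only the SAP's premise about how drop-outs enter the data, with loss confined to the post-period.

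**What to change.** Replace the sentence with: *Equal, non-informative dropout cancels only for rate ratios. For additive and logistic contrasts it can shrink, inflate or shift the DID, and unequal dropout biases all contrasts.* Describe differential dropout in B.4.4 as a source of bias, in line with B.4.6, and not only as a threat to generalizability. State that the B.4.6 comparisons cannot by themselves identify drop-outs.

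For each affected utilization and preventive-service outcome, report:

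1. the share of pre-period patients with no post-period contact, by group and year;
2. the rate-ratio DID beside any additive or logit DID;
3. the DID under bounds that treat no-contact patients as all non-users (kept as zeros) and as all drop-outs (removed from the post-period denominator), varied separately by group.

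In Oregon, use the linked Medicaid claims to estimate how many enrolled no-contact patients received care elsewhere, and anchor the bounds there. Carrying that share to uninsured patients or to other states is an assumption and should be labeled as one.

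The cost is one paragraph of SAP text and a few extra tables from data already held. The downside is a wider reported range for the affected outcomes.

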Aim 1. Compare pre-post health insurance status, primary care, mental health, and dental visits, and receipt of preventive services, as well as changes in payer mix among ADVANCE CHCs in states that did and did not expand Medicaid. *Hypothesis 1a:* CHCs in expansion states will experience an increase in overall visits and visits paid by Medicaid, relative to non-expansion states. *Hypothesis 1b:* The percentage of Medicaid visits in CHCs' overall payer mix will increase more significantly in expansion-states relative to non-expansion states.

Aim 2. Examine pre-post utilization of CHC services (including receipt of preventive services) by newly insured compared to already insured and uninsured patients. *Hypothesis 2:* Newly insured patients will have a significant increase in overall CHC visits compared to (a) already insured and (b) uninsured patients.

Aim 3: Measure pre-post changes in overall utilization of healthcare services and Oregon Medicaid expenditures among newly insured compared to already insured patients.

Hypothesis 3a: There will be an increase in utilization of CHC services and a decrease in use of services external to the CHCs (*e.g.*, emergency department) for newly insured patients, but these utilization rates will remain the same for already insured patients. *Hypothesis 3b:* There will be an initial increase, then plateau, in overall Medicaid expenditures among newly insured relative to already insured patients.

Data Sources

ADVANCE EHR Data. We used electronic health record (EHR) data from the Accelerating Data Value Across a National Community Health Center Network (ADVANCE) clinical data research network (CDRN) data warehouse. The ADVANCE CDRN is a unique ‘community laboratory’ for research with underrepresented populations that includes patients receiving care in safety net clinics. The ADVANCE CDRN data warehouse includes *integrated* longitudinal EHR data from several organizations. Data from two ADVANCE partners, OCHIN and Health Choice Network (HCN), were used in the PACE study. From the ADVANCE CDRN, we included CHC members ‘live’ on their EHR as of January 1, 2013: 225 primary care CHCs in 10 states that expanded Medicaid as of 1/1/2014 (California, Hawaii, Maryland, Minnesota, New Mexico, Ohio, Oregon, Rhode Island, Washington, and Wisconsin) and 134 primary care CHCs in 6 non-expansion states (Florida, Kansas, Missouri, North Carolina, Texas, Montana). We included Wisconsin as an expansion state because although they did not expand Medicaid to 138% FPL they opened enrollment to adults with eligibility criteria of 100% FPL and therefore behaved more like an expansion state. Montana did not expand Medicaid until after our study period (expanded 1/1/2016), which included a one-year pre- (1/1/13-12/31/13) and a two-year post-period (1/1/2014-12/31/2015). Analyses included >4 million ambulatory visits among patients aged 19-64 (expansion states: 2.6 million visits from 499,719 patients; non-expansion states: 1.5 million visits from 370,600 patients).

Linkage between EHR and Medicaid administrative data. Oregon Medicaid administrative data was linked to OCHIN Oregon clinics in the ADVANCE CDRN to assess the receipt of healthcare services outside the Oregon CHCs and all healthcare expenditures.

Study Population and Study Period

The overall study population was adults ages 19-64 throughout the study period, 2012-2015. Included patients had ≥ 1 ambulatory visit at an eligible facility in the study period. Included facilities provided adult primary care and were ‘live’ on OCHIN’s or HCN’s EHR system by the start of the study period (1/1/2012). EHR data were extracted on all eligible patients, encounters, and facilities.

Overall, study analyses included >4 million ambulatory visits among patients aged 19-64 (expansion states: 2.6 million visits from 499,719 patients; non-expansion states: 1.5 million visits from 370,600 patients).

We examined differences in utilization among patients newly gaining Medicaid coverage (*newly insured*), as compared to utilization among individuals who are already insured by Medicaid (*already insured*) and those who remain uninsured (*uninsured*). Additionally, in subpopulation analyses restricted to the state of Oregon (an expansion state), we link EHR data from Oregon CHC clinics to Oregon’s Medicaid administrative claims data to investigate post-expansion overall healthcare utilization and Medicaid expenditures among the newly insured as compared to the already insured. Inclusion and exclusion criteria were modified for some analyses; see below for details on specific paper analyses.

Table 2. Study population stratified by expansion status and state

2014 Expansion status	State	N facilities	N patients
Expansion	California	48	163,686
Expansion	Hawaii	2	10,075
Expansion	Maryland	24	15,297
Expansion	Minnesota	4	12,725
Expansion	New Mexico	25	63,488
Expansion	Nevada	3	2,326
Expansion	Ohio	15	55,537
Expansion	Oregon	121	261,166
Expansion	Rhode Island	59	38,946
Expansion	Washington	6	24,585
Non-expansion	Alaska*	1	3,820
Non-expansion	Florida	169	412,138
Non-expansion	Indiana**	10	16,200
Non-expansion	Kansas	9	8,047
Non-expansion	Missouri	3	16,461
Non-expansion	Montana	6	13,155
Non-expansion	North Carolina	21	39,726
Non-expansion	Texas	5	11,383
Non-expansion	Wisconsin***	8	20,593

*Alaska expanded Medicaid to 138% FPL on 9/1/2015 and was excluded from some analyses; **Indiana expanded Medicaid to 138% FPL on 2/1/2015 and was excluded from some analyses; ***Wisconsin expanded Medicaid from 0% to 100% on 1/1/2014 and therefore more closely resembled an ACA expansion state.

Wisconsin was considered an expansion state in analyses.

Stakeholder Engagement

The project team engaged a Patient Investigator ([name]) and a Clinician Investigator ([name], MD) throughout the duration of the project. These stakeholders advised the project team during the data analysis, manuscript development, and dissemination phases of the project. Their involvement was facilitated through ongoing training about the research process, collaboration with research team about data analyses challenges, data interpretation,

and manuscript development, and dissemination of research aims through presentations and blogging.

Data Analyses

Medicaid Expansion Produces Long-Term Impact on Insurance Coverage Rates in Community Health Centers

Full Citation	[name], N., Hoopes, M. J., Angier, H., Marino, M., Holderness, H., & DeVoe, J. E. (2017) Medicaid Expansion Produces Long-Term Impact on Insurance Coverage Rates in Community Health Centers. J Prim Care Community Health. 8(4):206-212.
Objective	Assess change in insurance coverage rates pre- and post-ACA in Medicaid expansion and non-expansion states for community health center patients.
Study Population	N=875,571 patients; Inclusion: ages 19-64 with ≥ 1 visit between 2012 and 2015. Setting: 412 primary care CHCs in 9 expansion and 4 non-expansion states.
Exclusion Criteria	Pregnant women
Independent Variables	Whether state had taken Medicaid expansion as of January 1, 2014.
Dependent Variables	Health care delivery: rates of billed encounters (all, primary care, new patient, established patient), receipt of preventive services (preventive medicine visits, immunizations, medications ordered). 1. Insurance type: uninsured, Medicaid-insured, privately-insured.
Covariates	Clinic-level: distributions of sex, age, race/ethnicity, primary language, federal poverty level. State-level: marketplace type, 2013 minimum wage, 2013 uninsured rate, 2013 unemployment rate.
Analysis Plan	Post- versus pre-expansion rate ratios within expansion group; difference-in-difference ratios (comparing post- versus pre-period changes between expansion states vs non-expansion states); and second year post- (2015) versus first year post-ACA (2014) rate ratios within expansion group.
Data Set Name	OCHIN: e:\sasroot\PPDA\P_Huguet_24mo
Code Location	OCHIN SAS server

Oregon Medicaid Expenditures After the 2014 Affordable Care Act Medicaid Expansion: Over-time Differences Among New, Returning, and Continuously Insured Enrollees

Full Citation	Springer, R., Marino, M., O'Malley, J. P., Lindner, S., [name], N., & DeVoe, J. E. (2018). Oregon Medicaid Expenditures After the 2014 Affordable Care Act Medicaid Expansion: Over-time Differences Among New, Returning, and Continuously Insured Enrollees. Med Care, 56(5) , 394-402.
Objective	To assess health care expenditures among Medicaid enrollees in the 24 months after Oregon's 2014 Medicaid expansions and examine whether expenditure patterns were different among the newly, returning, and continuously insured.
Study Population	Oregon adult Medicaid beneficiaries insured continuously from 2014 to 2015 who were either newly, returning, or continuously insured.
Exclusion Criteria	Our study population included adults aged 19-64 insured by Oregon Medicaid continuously from January 2014 through December 2015. We excluded patients without coverage on 1/1/2014 and those with coverage gaps during the study period. We excluded patients with dual Medicaid and Medicare eligibility and whose 2014-2015 eligibility did not depend on FPL (e.g. pregnant women). Of 622,513 adults aged 19-64 with any 2014 Medicaid enrollment, 230,602 (37%) remained in our sample.
Independent Variables	Insurance group, time, and their interaction terms, mean monthly expenditures.
Dependent Variables	standardized expenditures for inpatient care, prescription drugs, and total outpatient care in addition to subdivisions of outpatient: outpatient claims were classified as either emergency department, dental, mental and behavioral health, primary care evaluation, management, and procedures, specialist evaluation, management, and procedures, and primary care/specialist imaging or tests based on a hierarchical system involving procedure code, provider type, provider specialty, place of service, and associated costs.
Covariates	The patient's age, sex, racial and ethnic background, rural setting, and comorbidity level as assessed by the enhanced Charlson comorbidity index score.
Analysis Plan	Retrospective cohort study using inverse-propensity weights to adjust for differences between groups. We summarized enrollee

	utilization outcomes as mean monthly expenditures, running a separate (two-part) hurdle model for each type.
Data Set Name	NPAT, INPATIENT_Q42015, OUTPAT, OUTPATIENT_2015Q4, RX , RX_Q42015, SAMPLE, SAMPLE_with_weights FY_2015_FR_AND_CN_Table 5, Nov 2013 Fee Schedule – Excel, January 2014 Behavioral Health Fee Schedule, January 2014 Mental Health Fee Schedule – Excel
Code Location	Box at OHSU

Medicaid Coverage Accuracy in Electronic Health Records

Full Citation	Marino, M., H. Angier, S. Valenzuela, M. Hoopes, M. Killerby, B. E. Blackburn, N. [name], J. [name], B. Hatch, J. P. O' Malley and J. E. DeVoe (2018). Medicaid Coverage Accuracy in Electronic Health Records . Prev Med Reports 11 : 297–304.
Objective	To evaluate the validity of EHR data for monitoring longitudinal Medicaid coverage and assess variation by patient demographics, visit types, and clinic characteristics.
Study Population	Oregon Medicaid patients aged 18-64 years with a Medicaid ID or Medicaid insurance recorded in the OCHIN EHR ≥1 billed health care visit (excluding dental) from 184 Oregon CHCs in the OCHIN network linked to state Medicaid records during the study time period (1/1/2013–12/31/2014). N=135,514.
Exclusion Criteria	Patients with no Medicaid record on EHR who also did not have a Medicaid ID.
Independent Variables	Insurance cohort: (1) continuously Medicaid (Medicaid recorded at all visits); (2) continuously not Medicaid (Medicaid not recorded at any visit (patients could have Medicare, private, VA/Military, worker’s compensation, or no coverage); (3) Gained Medicaid: Medicaid not recorded for all visits in 2013 and Medicaid recorded at all visits in 2014; and (4) Discontinuously Medicaid: Any combination of visit coverage that did not follow the definitions above.
Dependent Variables	The primary outcome was agreement between EHR and Medicaid data in assigning patients to one of the four cohorts.
Covariates	Patient demographics (sex, age, race, ethnicity, language, household income represented as % FPL, urban/rural, number of common chronic conditions, and number of encounters), visit and provider types, and clinic-specific (department type and customers of OCHIN's billing service) characteristics. We included the following common chronic conditions assessed

	from diagnostic codes in the EHR: hypertension, diabetes, coronary artery disease, lipid disorder, and asthma/chronic obstructive pulmonary disorder.
Analysis Plan	Visit-level: agreement, prevalence-adjusted bias-adjusted kappa (PABAK), sensitivity, specificity, positive predictive value (PPV), and negative predictive value (NPV). Patient-level: 4x4 cross-tabulation, of insurance cohorts; two-stage logistic regression.
Data Set Name	PPDA Projects → InsuranceValidation → Data → CLEAN → patients.csv, patient_pre.csv, patient_post.csv, patient_ch.csv, encs_pre.csv, encs_post.csv, agree_no_final.csv Code is included under: PPDA Projects → InsuranceValidation → Final Code
Code Location	Box at OHSU

In Low-Income Latino Patients, Post-Affordable Care Act Insurance Disparities May Be Reduced Even More than Broader National Estimates: Evidence from Oregon

Full Citation	[name], J., S. R. Bailey, J. DeVoe, S. Cowburn, T. Kapka, T. V. Duong and M. Marino (2017). In Low-Income Latino Patients, Post-Affordable Care Act Insurance Disparities May Be Reduced Even More than Broader National Estimates: Evidence from Oregon. J Racial Ethn Health Disparities 4(3): 329-336.
Objective	To evaluate the association of Hispanic/Latino ethnicity and Spanish language preference with insurance status among a cohort of patients accessing community health centers (CHCs) in Oregon; prior to ACA implementation (2013) and 1-year post-ACA (2014). To determine if disparities in insurance coverage existed by race/ethnicity and language preference prior to ACA. If so, were such disparities mitigated by ACA implementation.
Study Population	N=49,392; Adults aged 21-79 in Oregon community health centers (CHCs) who had low income (<100% FPL), and at least 1 primary care encounter at a study clinic in 2009-2013, had to have at least 1 face to face primary care encounter.
Exclusion Criteria	
Independent Variables	Race/ethnicity, preferred language
Dependent Variables	Insurance status: Medicaid, Medicare, private insurance, uninsured.

	Categorized patients into the Medicaid and Medicare categories if patient had one or more encounters with these insurances.
Covariates	Age at beginning of study, sex, total number of primary care office visits in study period.
Analysis Plan	Chi-square for patient demographics; ANOVA to compare patient demographics by insurance group; GEE to account for correlation of patients nested with CHCs; DID/GEE to assess changes in odds of uninsured from pre-to post-ACA between Hispanic/Latino/Spanish, Hispanic/Latino/English, and non-Hispanic White cohorts.
Data Set Name	PPDA Projects → PACE → HeintzmanACA → 2014data.xls, heintzman_k_post_aca_comparison.xls Code is included under: PPDA Projects → PACE → [name] ACA → Code
Code Location	Box at OHSU

Medicaid's Impact on Chronic Disease Biomarkers: A Cohort Study of Community Health Center Patients.

Full Citation	Hatch, B., M. Marino, M. Killerby, H. Angier, S. R. Bailey, J. [name], J. P. O' Malley and J. E. DeVoe (2017). Medicaid's Impact on Chronic Disease Biomarkers: A Cohort Study of Community Health Center Patients. J Gen Intern Med 32 (8): 940-947.
Objective	To assess changes in biomarkers of chronic disease among community health center (CHC) patients who gained Medicaid coverage with the Oregon Medicaid expansion (2008–2011).
Study Population	OCHIN Medicaid patients within 3 chronic disease cohorts: patients with diabetes (N=608); patients with hypertension patients (N=1244); patients with hyperlipidemia patients (N=546). Patients gained Medicaid coverage between 2008-2011: Patients aged 1-+64 years; Non-pregnant, non-deceased; Uncontrolled biomarker result in EHR within 6 months before/after gained Medicaid coverage.
Exclusion Criteria	Pregnant women
Independent Variables	Insurance status, time, “spline” (slope change at 6 months) interactions between time and insurance and spline and insurance.
Dependent Variables	Biomarkers: 1. HbA1c

	
 2. Systolic blood pressure 3. Diastolic blood pressure 4. Lipids
Covariates	federal poverty level, comorbidities
Analysis Plan	Time to event assessing time from uncontrolled baseline measurement to follow up controlled measurement; Longitudinal analysis modeling the mean biomarker value over time; Logistic regression to estimate the odds of having a disease-specific medication ordered during study.
Data Set Name	PPDA Projects → PACE → CARDIACBiomarker → Data → all the files in there Code is under: PPDA Projects → PACE → CARDIACBiomarker → Rcode
Code Location	Box at OHSU

Uninsured Primary Care Visit Disparities Under the Affordable Care Act

Full Citation	Angier, H., M. Hoopes, M. Marino, N. [name], E. A. Jacobs, J. [name], H. Holderness, C. M. Hood and J. E. DeVoe (2017). Uninsured Primary Care Visit Disparities Under the Affordable Care Act. Ann Fam Med 15 (5): 434-442.
Objective	To assess changes in insurance coverage at community health center (CHC) visits after the Patient Protection and Affordable Care Act (ACA) Medicaid expansion by race and ethnicity
Study Population	
 1. N=870,319 2. 359 CHCs 3. CHC patients aged 19-64 years 4. Expansion states as of 1-1-14: California, 5. Hawaii, Maryland, Minnesota, New Mexico, Ohio, Oregon, Rhode Island, Washington, and Wisconsin 6. Non-expansion states as of 1-1-14: Florida, Kansas, Missouri, North Carolina, Texas, Montana
Exclusion Criteria	Pregnant women
Independent Variables	Expansion status (Medicaid expansion vs. non-expansion)
Dependent Variables	Health insurance type at each visit (Medicaid-insured, uninsured, privately-insured)
Covariates	
Analysis Plan	
 1. Difference-in-difference (DID) 2. Difference-in-difference-in-difference (DDD) 3. GEE models
Data Set Name	
HA_disp_analysis_long.sas7bdat
 
HA_disp_monthly_analysis_set.sas7bdat

Code Location	OCHIN archive server

A Cohort Study of Public Health Insurance Coverage Loss among Oregon Adolescents

Full Citation	Angier, H., C. J. Tillotson, L. S. Wallace, M. Marino, J. P. O' Malley, A. Sumic, L. Baker, C. Nelson, N. [name], A. Suchocki, H. Holderness and J. E. DeVoe (2018). A Cohort Study of Public Health Insurance Coverage Loss among Oregon Adolescents. J Health Dispar Res 11(1).
Objective	The purpose of this study was to identify the sociodemographics of adolescents transitioning to young adulthood who lost public health insurance which could inform future health policies for this vulnerable population.
Study Population	Oregon adolescents (17-19 years of age) with public coverage [January 1, 2011-December 31, 2013 (n=51,988)].
Exclusion Criteria	Missing information on urban/rural residency status (n=4,025) and/or family income (n=973).
Independent Variables	Sociodemographic characteristics: age, sex, race, ethnicity, language, percentage of federal poverty level based on family income and size, history of a healthcare visit to a community health center included in the OCHIN network during the study period (2011-2013), and urbanicity.
Dependent Variables	OHP Coverage
Covariates	
Analysis Plan	Time to Event: to determine association of coverage loss with sociodemographic characteristics.
Data Set Name	analysis_nogaps_01202016.sas7bdat dmapochin13_nogaps_01202016.sas7bdat Code is under: R:\Active projects\IMPACCT\Reports\Data analysis and results\Teen Transition\[name]\SAS Code and Programs\5d_MV Models nogaps 01112016.sas
Code Location	OCHIN archive server

A New Role for Primary Care Teams in the United States After “Obamacare”: Track and Improve Health Insurance Coverage Rates.

Full Citation	DeVoe, J. E., H. Angier, M. Hoopes and R. Gold (2016). A New Role for Primary Care Teams in the United States After “Obamacare”: Track and Improve Health Insurance Coverage Rates. Family Medicine and Community Health 4(4): 63-67(65).
Objective	Describe efforts to longitudinally track health insurance rates using data from the electronic health record (EHR) of a primary care network and to use these data to support practice-based insurance outreach and assistance.

Study Population	OCHIN member clinics and patients.
Exclusion Criteria	Not an OCHIN member clinic or patient.
Independent Variables	NA
Dependent Variables	Insurance coverage in EHR.
Covariates	NA
Analysis Plan	NA
Data Set Name	NA
Code Location	NA

The Impact of the Affordable Care Act Medicaid expansion on visit rates for a patient population with diabetes or pre-diabetes in safety net health centers

Full Citation	[name], N., R. Springer, M. Marino, H. Angier, M. Hoopes, H. Holderness and J. E. DeVoe. (2018) The Impact of the Affordable Care Act Medicaid expansion on visit rates for a patient population with diabetes or pre-diabetes in safety net health centers. J Am Board Fam Med. 31(6):905-916
Objective	To compare clinic-level uninsured, Medicaid-insured, and privately insured visit rates within and between expansion and non-expansion states prior to and after the ACA Medicaid expansion among the three cohorts of patient populations; and, to assess whether there was a change in clinic-level overall, primary care, preventive care visits, and diabetes screening rates in expansion versus non-expansion states from pre- to post-ACA Medicaid expansion.
Study Population	198 primary care community health centers: Non-pregnant patients aged 19-64 with ≥1 ambulatory visit between 01/01/2012-12/31/2015 (n=483,912 in expansion states; n=388,466 in non-expansion states).
Exclusion Criteria	Pregnant women
Independent Variables	Expansion status
Dependent Variables	1. Insurance coverage 2. Healthcare services
Covariates	Health insurance status, sociodemographic variables, urban/rural, state-level factors.
Analysis Plan	
 • Rate Ratios • Difference in Difference • GEE/Poisson models with sandwich variance estimators • Clustered models by CHC

	
 • Exchangeable covariance structure • Sensitivity analysis
Data Set Name	STATES, ELIGIBLE FACILITIES, ENCOUNTERS_AV1215_pipe, PAT_CONSORT_08312016, FAC_URBRUR
Code Location	BOX at OHSU

Prescription Opioid Use Patterns, Use Disorder Diagnoses, and Addiction Treatment Receipt after the 2014 Medicaid Expansion

Full Citation	Springer, R., M. Marino, S. Bailey, H. Angier, J. O’Malley, M. Hoopes, S. Lindner, J. DeVoe and N. [name]. Prescription Opioid Use Patterns, Use Disorder Diagnoses, and Addiction Treatment Receipt after the 2014 Medicaid Expansion. Resubmitted 12/18 to Addiction.
